5. PROCEDURES

5.1. [DETERMINATION] Study procedures. Using lay language, provide a complete description of the study procedures, including the sequence, intervention, or manipulation (if any), drug dosing information (if any), blood volumes and frequency of draws (if any), use of records, time required, and setting/location. If it is available: Upload a study flow sheet or table to **Zipline**.

For studies comparing standards of care: It is important to accurately identify the research procedures. Review the section titled, "When to describe risks for studies evaluating medically recognized standards of care" in the [Identifying and Describing Reasonably Foreseeable Risks in Research](#) guidance and the draft guidance from the federal Office of Human Research Protections, "[Guidance on Disclosing Reasonably Foreseeable Risks in Research Evaluating Standards of Care](#)"; October 20, 2014.

Information about pediatric blood volume and frequency of draws that would qualify for expedited review can be found in this [reference table](#) on the Seattle Children's IRB website.

We plan to work with the internal medicine hospitalist group to conduct this study. There will be two lead hospitalists of contact at Montlake, Harborview and Northwest each. The screening hospitalists screen patients who need to be admitted to the hospital as their regular practice. In the meantime, they will screen eligible subjects who meet our inclusion/exclusion criteria.

Once eligible subjects are identified, screening hospitalists or admitting hospitalists will explain the rationales of this study and obtain informed consent. This process will be part of the standard admission interview which happens within one hour of admission. The interview happens either in the emergency room or hospital room, depending on whether a hospital room is immediately available.

This feasibility trial is designed as single-arm and mainly to investigate safety (no excessive hypoglycemia compared to standard of care). We will examine hyperglycemia as a secondary endpoint. We do not include a control arm in this study for comparison. The reason is it takes too many subjects to have enough power to detect potential excessive hypoglycemia (we plan a randomized study of a larger sample size after this feasibility trial to further exam the glycemic and clinical outcomes). For a feasibility trial, we would like to know if it is safe by testing on a small number of subjects.

This consent process will be part of the admission interview which happens either in the emergency room or hospital room. If subjects are not able to consent, the hospitalists will obtain consent from their legally authorized representatives' (LAR) in person or on the phone.

Patients who report low appetite 25% or less, NPO for 24 hours before admission, or planned NPO for 24 hours after admission will be excluded because they have risk to be overdosed by our predicted insulin doses. If patients had a significantly decreased level of consciousness that the study team does not think they are going to eat right after admission, they will also be excluded from this trial.

Hospitalists that are going to enroll subjects will join a one-hour launch meeting when the PI will introduce the study procedure and how to use the online calculator. There will be a session of questions and answers. At the end of the meeting, we will assess whether the hospitalists feel comfortable to start enrolling patients. If they do not feel ready, we will plan further meetings before they start the enrollment.

Hospitalist Enrollment

If subjects agree to join this trial, hospitalists will go to our online calculator to calculate the initial insulin dosing regimen (<https://inpatientinsulin.com>). The questions in the online calculator will be asked during the interview with the subjects. Some information required in the calculator may be obtained from a caregiver rather than the subject if the caregiver knows the information better. In this case, the hospitalists will obtain consent from the subject or LAR before receiving health information from a caregiver. Hospitalists will confirm whether the caregiver knows the required information well, as the standard of care. If hospitalists could not obtain reliable information within 20% range (plus minus 10%), this subject will not be enrolled. For example, if a subject's home daily insulin dose cannot be confidently narrowed within the 36 - 44 units range, This subject will not be enrolled using home daily insulin dose of 40 units in the calculator.

Resident Enrollment

If patients are admitted to the teaching service (residents' service), attending hospitalists will obtain informed consents and calculate the initial insulin doses personally. Attending hospitalists will work with residents closely to do standard insulin adjustments. When changing shifts, attending hospitalists will sign out to the next attendings.

PI Enrollment

An alternative way of enrollment is that PI: [name] obtains informed consents and calculates the initial insulin doses. The PI will call the attending hospitalist (and the resident if admitted to teaching service) assigned to the patient to confirm that the hospitalist (and resident) will remain on-shift until the insulin order is placed. The PI

will inform the hospitalist (or resident) that the PI will be recruiting and consenting their patient for a study. They will discuss whether the PI or the hospitalist (or resident) will be placing the order.

After the dosage is calculated by the PI using the calculator, the PI will text the dosage to the hospitalist (and resident) using Epic chat and confirm that the PI or the hospitalist (or resident) will place the order, whoever was agreed upon in the earlier phone call. If the hospitalist (or resident) places the order, the PI will check the order was placed correctly. If the PI places the order and the hospitalist (or resident) has already placed it, the PI will delete the existing order. After the initial dose, the hospitalist (or resident) will continue care as usual (under the supervision of a hospitalist if a resident).

Standard Care

After admission, primary providers will monitor their point-of-care capillary (POC) blood glucose (BG) and laboratory venous BG. After the first dose (by the calculator) is given, providers will continue adjusting insulin doses as the current standard of care. As the current standard of care, POC-BG are checked at least before 3 meals, at bedtime, and 2-3AM, so subjects will get their blood glucose checked within 5-6 hours after the first calculator-determined insulin dose. This is the same time frame as for patients given standard of care insulin doses. The 2-3AM blood glucose check is in the UW order set and will be ordered for all subjects in this trial. The rest of patient care will be no different from standard of care.

Other Procedures

We plan to extract data from the inpatient Electronic Medical Record (EMR), including demographic characteristics (age, gender, race, weight, height), diabetes history (diabetes type, home antidiabetic medications), vital signs, laboratory measurements (POC BG and laboratory venous BG, latest hemoglobin A1c, renal function), interventions (inpatient insulin dose and modality, glucocorticoid, pain medication, surgery or procedure), nutrition status (oral intake, tube feed, intravenous dextrose), and hospital admission/discharge dates.

Our UW observational cohort (STUDY00015475) has 1/140 patients (0.7%) who had hypoglycemia < 54 mg/dL during the first 24 hours of hospitalization. We think (and from prior inpatient glycemic trials) 3% increase (which means 3.7%) is considered clinically significant increase, so among these 85 subjects there cannot be more than $85 \times 3.7\% = 3.15$ subjects that develop hypoglycemia < 54 mg/dL. So, if we find more than 3.15 patients (round to 4) who develop BG < 54 during the recruitment, that is more than 3% increase. Because this is the first feasibility trial to apply the calculator on patients, we plan to enroll 10 subjects first, to demonstrate the calculator dose does not cause hypoglycemia (≤ 54 mg/dL). After these 10 participants are recruited, we will review and analyze these data. Then we will apply for a modification to increase the sample size.

To examine the feasibility, the specific outcomes that will be measured are hypoglycemia (< 54 mg/dL), mean BG during the first 24 hours of hospitalization, and hyperglycemia (≥ 300 mg/dL), compared to our UW observational cohort ([STUDY00015475](#)).

The International Hypoglycemia Study Group defined three levels of hypoglycemia for the purpose of standardized reporting: BG < 70 mg/dL (level 1), < 54 mg/dL (level 2), < 40 mg/dL (level 3) [1]. Centers for Medicare & Medicaid Services (CMS) use the same definition to capture hospital glycemic data [2]. BG < 54 mg/dL was defined as clinically significant hypoglycemia and used in prior inpatient glycemic trials [3].

For statistical analyses, trial subjects (single-arm study with utilization of the insulin calculator) will be compared with the UW observational cohort (STUDY00015475) where standard of care was used (mostly by physicians' experience). The primary endpoint is hypoglycemia < 54 mg/dL. The secondary endpoint is mean BG during the first 24 hours of hospitalization and hyperglycemia (≥ 300 mg/dL).

Reference

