If this application involves the use of a HUD “humanitarian” device: describe whether the use is for “on-label” clinical patient care, “off-label” clinical patient care, and/or research (collecting safety and/or effectiveness data).

Patients with hyperglycemia have heterogeneous physiologies and their insulin requirements are highly varied. The currently available algorithms cannot precisely predict their initial insulin doses. More importantly, there is no algorithm so far that is supported by evidence.

We hypothesize that standardized algorithms using multiple factors can more precisely predict patients' individual insulin requirements on hospital admission. Our prospective study (STUDY00015475) at the University of Washington (UW) built an insulin calculator for patients with T2DM on home insulin and adequate oral intake peri-admission (sample size 140). Using multivariable regression models, our predicted daily insulin doses have a correlation factor of 0.793 with their actual insulin requirements. No outlier that would be severely overdosed was noted in our observational cohort.

The factors used to predict insulin requirement are patients' oral intake plan, home insulin dose, first blood glucose value on presentation, inpatient glucocorticoid dose, systemic inflammatory response syndrome (SIRS), dose and timing of last long-acting insulin prior to admission. Our online calculator (<https://inpatientinsulin.com>) will be used to calculate the initial insulin dosing regimen.

Our calculator is based on observational studies, so it remains unclear whether it can help clinicians achieve recommended glycemic targets. We propose using these calculators can achieve inpatient glycemic goal of 100-180 mg/dL (American Diabetes Association's guidelines 2023) faster than the standard of care with less manual adjustments. Before we perform a study of a large sample size, it is important to test whether using this calculator in the clinical setting is safe. This study is a feasibility trial to mainly investigate its safety (no excessive hypoglycemia). We will also examine whether using this calculator decreases hyperglycemia. The trial will provide opportunities to adjust the algorithms before the randomized controlled trial.

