It is not necessary to summarize all the discussion that has led to the development of the study protocol. The IRB is interested only in short summaries about experiences or preliminary work that suggest the study is feasible and that risks are reasonable relative to the benefits. Examples: Your team has already conducted a Phase 1 study of an experimental drug which supports the Phase 2 study being proposed in this application; your team has already done a small pilot study showing that the reading skills intervention described in this application is feasible in an after-school program with classroom aides; your team has experience with the type of surgery that is required to implant the study device; the study coordinator is experienced in working with subjects who have significant cognitive impairment.

Our proof-of-concept study at UC Davis identified several factors associated with initial insulin requirements for patients with history of diabetes mellitus (DM) and any BG value ≥ 180 mg/dL during the first 24 hours of hospitalization [1]. Then our prospective study at the University of Washington (UW) built insulin calculators for patients with different types of DM. For the study population of this trial, patients with T2DM or steroid-induced DM who take insulin prior to admission, our predicted daily insulin dose has a correlation factor of 0.795 with their actual insulin requirements. In addition, we excluded outliers (who have low oral intake before or after admission) so the rest of patients show no severe overdose in our cohort.

1. [name] HH, Surampudi P, Sood A. Determinants of initial insulin therapy for hospitalized patients with diabetes mellitus. J Diabetes Complications. 2022 Oct;36(10):108307.

1.8.c. Subject matter expertise. Is the study a clinical trial and/or does the study involve use of a drug, biologic, botanical, nutritional supplement and/or is the study otherwise considered to be greater than minimal risk to subjects?

- ☐ **No** → Answering this question is optional.
- ☒ **Yes** → Provide the name, degree(s), and contact information (e.g., email, phone number) of someone with appropriate expertise in the subject matter described in the objectives and design of this study. The individual should be unaffiliated with the study and have no other apparent conflict of interest. The individual may be associated with the UW or external to the University. Ensure the individual is aware they may be contacted by HSD.

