2. PARTICIPANTS

2.1. [DETERMINATION] Participants. Describe the general characteristics of the subject populations or groups, including age range, gender, health status, and any other relevant characteristics.

Document Date & Version

06.29.2023

Version 4.6

APPLICATION IRB Protocol

Researcher Date & Version

mm/dd/yyyy

Version x.x

Page 7 of 55

We plan to recruit adult patients who are admitted to UW Montlake, Harborview and Northwest hospitals with history of type 2 diabetes mellitus on insulin therapy prior to admission. Because we work with the internal medicine hospitalist group, these patients are admitted for various non-critical acute illnesses from the emergency room. They can also be non-emergent admissions from the clinics. The obstetrics ward tends to use a different glycemic goal than other inpatient populations, so we exclude patients admitted to obstetrics ward. Our prior observation cohort did not include patients admitted for elective surgery or procedure, so our calculator has not been validated in this population.

2.2. [DETERMINATION] Inclusion and exclusion criteria.

2.2.a. Inclusion criteria. Describe the specific criteria that will be used to decide who will be included in the research from among interested or potential subjects. Define any technical terms in lay language.

1. Patients who are admitted to University of Washington Medical Center – Montlake, Harborview and Northwest hospitals
2. Aged ≥ 18 years
3. With history of type 2 or steroid-induced diabetes mellitus
4. Receiving insulin therapy prior to admission

2.2.b. Exclusion criteria. Describe the specific criteria that will be used to decide which of the subjects who meet the inclusion criteria listed above will be excluded from the research. Define any technical terms in lay language.

1. Patients who are admitted to ICU or obstetrics ward
2. Patients who are admitted for elective surgery or procedure
3. Patients who present with diabetic ketone acidosis, hyperosmolar hyperglycemic state or need IV insulin infusion
4. Patients who have no meal intake for 24 hours prior to admission, planned nothing per oral (NPO) during the first 24 hours after admission
5. Patients who report low appetite (25% or less) on admission or have a significantly decreased level of consciousness that study team does not think they are going to eat right after admission
6. Patients who receive enteral feeding after admission

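### The 140-patient comparator is described as excluding patients who ate little after admission, while the trial keeps such subjects, so the mean BG and BG ≥ 300 comparisons may be biased, more likely towards the calculator

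*Combined protocol and SAP*

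**What the plan says.** Every outcome is judged against one historical group. Section 5.1 states that "trial subjects (single-arm study with utilization of the insulin calculator) will be compared with the UW observational cohort (STUDY00015475"), and the hypoglycemia benchmark comes from the same source: "Our UW observational cohort (STUDY00015475) has 1/140 patients (0.7%) who had hypoglycemia < 54 mg/dL during the first 24 hours of hospitalization".

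Two places describe how that group was formed. Section 1.5 says that the earlier study "built an insulin calculator for patients with T2DM on home insulin and adequate oral intake peri-admission (sample size 140"). Section 1.8.b adds that "we excluded outliers (who have low oral intake before or after admission) so the rest of patients show no severe overdose in our cohort".

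Trial eligibility (section 2.2.b) works from what is known at admission. It excludes patients with no meals in the preceding 24 hours, patients with a plan to be NPO for the next 24 hours, "Patients who report low appetite (25% or less) on admission", and patients whose reduced consciousness makes the team doubt that they will eat. Section 5.1 places this assessment in the admission interview, within an hour of admission. The withdrawal rules in section 10.8 do not cover a subject who is enrolled and then eats little.

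Section 1.5 plans an independent two-sample t test for mean BG and Pearson's chi-squared test for BG ≥ 300, with no adjustment stated. Section 5.1 lists "nutrition status (oral intake, tube feed, intravenous dextrose") among the data to be extracted, but no analysis uses it.

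**The concern.** On the more natural reading of section 1.8.b, the cohort lost patients because of intake after admission: they are called outliers, the wording is low intake rather than a plan not to eat, and their removal is given as the reason why no severe overdose remains. A trial that enrols within the first hour cannot foresee everyone who will eat poorly. It will dose and count some patients of a kind that the comparator has dropped.

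Section 5.1 says that low-intake patients risk being overdosed by the predicted dose, which points to lower glucose in them. If they sit in the trial group only, they pull down its mean BG and its share with BG ≥ 300, and part of an apparent improvement could be selection. These two outcomes are the only efficacy evidence that this study carries forward to the planned randomized trial.

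**Working it through.** **1. The plan's own figure.** Inputs from section 5.1: 1/140 = 0.714%, a margin of 3 percentage points, 85 subjects. 85 × 3.7% = 3.145, which matches the stated 3.15. With the unrounded rate, 85 × (1/140 + 0.03) = 3.157. Both round up to 4 events.

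**2. Selection side by side.**

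| | Cohort (1.5, 1.8.b) | Trial (2.2.b, 5.1, 10.8) |
|---|---|---|
| Before admission | low intake removed | no meals for 24 h excluded |
| At admission | not described | reported appetite ≤ 25% excluded |
| After admission | low intake removed; how it was judged is not stated | planned NPO or expected not to eat excluded; actual low intake kept |

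**3. Mean BG if the calculator has no effect.** The documents give no SD, no significance level and no share of low eaters. Assumed: SD 50–70 mg/dL, two-sided 5% test, a share f of trial subjects who eat little, and 24-hour means d mg/dL lower in them.

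Bias = f × d. With d = 40, f = 5%, 10% and 20% give 2, 4 and 8 mg/dL.

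SE = SD × √(1/85 + 1/140) = SD × 0.1375, that is 6.88, 8.25 and 9.63 for SD 50, 60 and 70.

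The chance of a significant result favouring the calculator is 1 − Φ(1.96 − bias/SE):

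| Bias (mg/dL) | SD 50 | SD 60 | SD 70 |
|---|---|---|---|
| 0 | 2.5% | 2.5% | 2.5% |
| +2 | 4.8% | 4.3% | 4.0% |
| +4 | 8.4% | 7.0% | 6.1% |
| +8 | 21.3% | 16.1% | 13.0% |
| −1 | 1.8% | 1.9% | 2.0% |
| −4 | 0.6% | 0.7% | 0.9% |

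The negative rows show low eaters running 20 mg/dL higher, with f = 5% and 20%.

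**4. BG ≥ 300.** Assumed cohort rate p = 15–35%, and low eaters at a ratio rr of that rate. Trial rate = p × (1 − f + f × rr). With rr = 0.5 the spurious fall runs from 0.4 points (p = 15%, f = 5%) to 3.5 points (p = 35%, f = 20%). The chance of a significant result favouring the calculator runs from 3.0% to 7.6%, against 2.5%. With rr = 1.2 the difference reverses, by 0.15 to 1.4 points.

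**5. Primary limit.** Restoring patients to the cohort could only raise the limit to 5 if the benchmark exceeded 4/85 − 0.03 = 1.71%. One restored event is not enough: at most 2/141 = 1.42%, giving 85 × (0.0142 + 0.03) = 3.76, still 4. Two events among 35 restored patients give 3/175 = 1.714% and 85 × 0.04714 = 4.007, which just crosses; two among 36 give 3.999 and do not.

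In the trial, suppose that 10% of subjects are low eaters with a 5% event rate (assumed) and the rest are at 1/140. The overall rate is 0.9 × 0.714% + 0.1 × 5% = 1.14%, and the binomial chance of 4 or more events in 85 rises from 0.3% to 1.7%. The mismatch makes the safety rule slightly stricter.

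**The case against.** The strongest reply is that section 1.8.b is one sentence about a study that the reader cannot see. It does not say whether intake after admission was observed or only planned. The trial's planned-NPO exclusion, with the same overdose rationale, could be that rule restated. The calculator takes the intake plan as an input, and the earlier study was prospective, so plans may well have been recorded. This reading is possible. It is less natural than the other, but only the team can settle it, and if it is right the mismatch disappears.

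The direction is also inferred. Low eaters may be sicker and run higher, and low glucose caused by too large a calculator dose is partly a treatment effect rather than selection. Both points stand, so the size and sign above are illustrations. At 5% low eaters the distortion is small.

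It can be added that section 2.2.b already excludes some conditions that arise after admission (enteral feeding, acute kidney injury needing dialysis). That is true, but neither removes a subject who simply eats little. Keeping such subjects is right for a safety endpoint, and the missing withdrawal rule is not a fault.

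A reader might infer more: that the plan will produce a false finding of benefit, or that the hypoglycemia limit is too lax. The documents support neither. They give no low-eater share, SD or BG ≥ 300 rate from which a false finding could be predicted, and for BG < 54 the likely error runs in the cautious direction.

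**Conclusion.** The concern holds in a limited form. As described, the comparator excludes low intake after admission and the trial does not, so the groups for mean BG and BG ≥ 300 are not selected alike and the planned unadjusted tests may be biased. The calculator is the more likely beneficiary. With 5–20% low eaters running 40 mg/dL lower, the bias is 2–8 mg/dL, and the chance of a spurious significant benefit is about 4–21% rather than 2.5% for an SD of 50–70. All of these inputs are assumptions, and the sign reverses if low eaters run higher. The 4-event limit stands. Only secondary comparisons in a feasibility trial are affected, so this is a minor correction, but a cheap one that is worth making.

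**What to change.** Settle this before any trial outcome is compared with the cohort. That means before the interim look, for which section 5.1 says: "After these 10 participants are recruited, we will review and analyze these data".

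1. State in section 1.8.b how low intake after admission was judged in STUDY00015475. If only plans known at admission were used, say so; no re-analysis is needed.
2. Otherwise, apply the section 2.2.b criteria to STUDY00015475 using admission-time information only, and restore patients removed solely for low intake after admission. Use that set as the comparator for mean BG and BG ≥ 300. Report how many were restored and how many of them had BG < 54, beside the unchanged 4-event limit.
3. If admission appetite or NPO plans were not recorded for the removed patients, keep the 140. Add a sensitivity analysis of mean BG and BG ≥ 300 that applies the cohort's intake rule to trial subjects, using the oral intake already extracted. Label it as conditioning on intake after dosing. Every BG < 54 still counts towards the limit.

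The cost is one sentence, or one re-analysis of the team's own data with a short protocol note. No subjects are added.

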The specific outcomes that will be measured are hypoglycemia (< 54 mg/dL), mean BG during the first 24 hours of hospitalization, and severe hyperglycemia (≥ 300 mg/dL). Hypoglycemia (< 54 mg/dL) cannot be 3% higher than the UW observational cohort (explained in section 5.1). Independent two-sample t test will be used to analyze mean BG and Pearson's chi-squared test will be used to analyze the occurrence of hyperglycemia (≥ 300 mg/dL), compared to the UW observational cohort ([STUDY00015475](#)). We plan to work with hospitalists at UW hospitals to use this calculator on hospital admissions for patients with T2DM on home insulin.

There is lack of large interventional studies to demonstrate whether improving inpatient glycemic control changes patients' clinical outcomes. The randomized controlled study we planned after this feasibility trial will explore whether using this calculator improves clinical outcomes.

- 1.6. **[DETERMINATION] Study design.** Provide a one-sentence description of the general study design and/or type of methodology.

Your answer will help HSD in assigning applications to reviewers and in managing workload. Examples: a longitudinal observational study; a double-blind, placebo-controlled randomized study; ethnographic interviews; web scraping from a convenience sample of blogs; medical record review; coordinating center for a multi-site study.

This is a clinical trial that uses the insulin dosing calculator for patients who are admitted to the UW hospitals

- 1.7. **[DETERMINATION] Intent.** Check all the descriptors that apply to your study. You must check at least one box.

This question is essential for ensuring that your application is correctly reviewed. Please read each option carefully.

Check all that apply	Descriptor
	Class project or other activity whose purpose is to provide an educational experience for the researcher (for example, to learn about the process or methods of doing research).
	Part of an institution, organization, or program's own internal operational monitoring.
	Improve the quality of service provided by a specific institution, organization, or program.

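### The limit of 4 events in 85 carries no confidence bound: at the plan's own unacceptable rate of 3.7% it is not reached 61% of the time, so 1 to 3 events cannot be read as showing no excess hypoglycemia

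*Combined protocol and SAP*

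**What the plan says.** Section 5.1 states: "The primary endpoint is hypoglycemia < 54 mg/dL". The reference is the earlier observational cohort, which had "1/140 patients (0.7%) who had hypoglycemia < 54 mg/dL during the first 24 hours of hospitalization". A "3% increase (which means 3.7%) is considered clinically significant increase", and this is turned into a count: "so among these 85 subjects there cannot be more than" 85 × 3.7% = 3.15 with the event. The decision sentence follows: "if we find more than 3.15 patients (round to 4) who develop BG < 54 during the recruitment", the increase is taken to exceed 3 points. Section 10.1 repeats the passage.

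Section 1.5 gives the requirement in words: "Hypoglycemia (< 54 mg/dL) cannot be 3% higher than the UW observational cohort". Section 5.1 describes the trial as "mainly to investigate safety (no excessive hypoglycemia compared to standard of care".

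Section 1.5 names a two-sample t test for mean glucose and a chi-squared test for values of 300 mg/dL or more. Section 5.1 says that trial subjects will be compared with the cohort, but names no method for the primary endpoint. The documents give no significance level, sidedness, confidence level or error rate for it.

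**The concern.** An observed proportion below a limit does not show that the true rate is below it. The plan's limit is set where about three events are expected if the true rate equals the rate it calls unacceptable. Three or fewer events is then a likely result even when the unwanted excess is present.

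This is the only criterion given for the trial's main question. If 1, 2 or 3 events occur and the report describes hypoglycemia as not excessive, that statement would go beyond the data.

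**Working it through.** **Inputs, from section 5.1 (repeated in 10.1).** n = 85; cohort rate 1/140 = 0.714%; margin 3 points; unacceptable rate 3.7%; limit reached at 4 events.

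**The plan's own figure.** 85 × 0.037 = 3.145, or unrounded 85 × (1/140 + 0.03) = 3.157. Both agree with the stated 3.15. Since 3/85 = 3.53% lies below 3.7% and 4/85 = 4.71% above it, the rule is a comparison of the observed proportion with 3.7%.

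**Chance that the limit is not reached.** For X ~ Binomial(85, p), this is P(X ≤ 3). At p = 0.037 the terms for 0, 1, 2 and 3 events are 0.0406 + 0.1325 + 0.2138 + 0.2273 = 0.614. At the unrounded 3.714% the sum is 0.611.

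| True rate | P(3 or fewer of 85) |
|---|---|
| 1/140 | 99.7% |
| 3.7% | 61.4% |
| 5% | 38.0% |
| 6% | 24.3% |
| 8% | 8.4% |

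The probability falls to 50% at a true rate of about 4.3% and to 5% at about 8.9%. Checking the count throughout recruitment changes nothing, because reaching 4 at any time is the same event as having 4 or more by subject 85.

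**What each result excludes.** These are exact (Clopper-Pearson) upper bounds. The one-sided 95% level is an assumption, so 97.5% is shown beside it. For 0 events the bounds are 1 − 0.05^(1/85) = 3.46% and 1 − 0.025^(1/85) = 4.25%.

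| Events of 85 | One-sided 95% | One-sided 97.5% |
|---|---|---|
| 0 | 3.5% | 4.25% |
| 1 | 5.5% | 6.4% |
| 2 | 7.2% | 8.2% |
| 3 | 8.9% | 10.0% |

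At one-sided 95% only 0 events excludes 3.7%. At 97.5% no result does.

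**How often 0 events would occur.** At 3.7%: 0.963^85 = 4.1%. At the cohort rate: (139/140)^85 = 54.4%, so a calculator as safe as the cohort would miss a 0-event criterion 45.6% of the time.

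**The benchmark itself.** The exact two-sided 95% interval for 1/140 is 0.02% to 3.9%, which contains 3.7%. The rule treats the cohort rate as known.

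**The case against.** Several counter-arguments have force.

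- **The rule is written in one direction only.** Sections 5.1 and 10.1 say what 4 events means. They do not say that 3 or fewer establishes safety, and reading the count during recruitment also fits a monitoring limit. A reader might infer that the calculator will be declared safe at 3 or fewer. That is an inference from the ceiling, not a stated conclusion. It remains true that no other criterion is given for the primary endpoint, and that section 1.5 words the ceiling as a requirement.
- **A reader might take the count as the gateway to the randomised trial.** Sections 1.5 and 5.1 say that such a trial is planned afterwards and that the algorithms may be adjusted first. No go/no-go rule ties it to this count.
- **A reader might conclude that harmful calculators generally escape the limit.** From the unacceptable rate upwards, escape is more likely than detection only between 3.7% and about 4.3%. At 5% and above, the limit is usually reached.
- **The trial is a feasibility study.** Section 1.7 ticks the exploratory category, and section 5.1 concedes that adequate power would take too many subjects. That remark explains the absence of a control arm; it does not limit what may be concluded about safety.
- **There are other safeguards.** Ten subjects are enrolled first and reviewed, but no numerical rule is given. At a true 3.7%, 0 of 10 occurs 68.6% of the time (0.963^10), and its one-sided 95% upper bound is 25.9%. The data and safety monitoring plan in section 10.6 is a separate upload that is not among the documents, so a further rule there cannot be ruled out. Sections 1.5, 5.1 and 10.1 would still need to say how the primary endpoint is concluded.

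**Conclusion.** The concern holds in a limited form. The four-event limit has no interval or test behind it, and at the plan's own unacceptable rate it is not reached 61% of the time. That figure needs only the documents' numbers and independent subjects with a common event rate. With 1 to 3 events, a true rate of 3.7% is not excluded at one-sided 95%, and the data remain compatible with rates up to 5.5%, 7.2% or 8.9%.

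Two stronger readings fail. It is not true that no result could be informative: 0 of 85 excludes a fixed 3.7% at one-sided 95%, although not at 97.5%. Nor would 0 events by itself prove an excess of less than 3 points over the cohort, because 3.7% is built on one event in 140 and that uncertainty is ignored.

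**What to change.** 1. Keep 85 subjects and keep four events as an alert limit. In sections 5.1 and 10.1, state beside it that at a true rate of 3.7% the limit is not reached 61% of the time.
2. Report the primary endpoint with its exact (Clopper-Pearson) upper bound, and name the confidence level in advance. One-sided 95% is used here only because the documents give none.
3. In sections 1.5, 5.1 and 10.1, fix the wording for each result. With 1 to 3 events: alert limit not reached, a rate of 3.7% not excluded, with the upper bound (5.5%, 7.2% or 8.9% at one-sided 95%). With 0 events: a fixed 3.7% benchmark is excluded at one-sided 95% (bound 3.5%), but not at 97.5% (4.25%).
4. State that 3.7% is a fixed benchmark derived from 1/140 (exact 95% interval 0.02% to 3.9%), so that excluding it is not presented as proof of a less than 3-point excess over the cohort.

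This changes wording and adds one interval; it needs no extra subjects. The cost is a less favourable claim with 1 to 3 events, and a 46% chance that a calculator as safe as the cohort would not meet the 0-event criterion. It also leaves 85 too few to settle the question reliably. Excluding 3.7% at one-sided 0.05 with at least 80% power at a true 1/140 would take 168 subjects with at most 2 events; at one-sided 0.025 and at least 90% power it would take 235 with at most 3. Those error rates are assumptions, given only for scale.
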